12.2 Quality Control

12.2.1 Definition

Quality control is defined as operational techniques and activities performed under a quality assurance system, such as monitoring, which is intended for verifying that the study-related activities meets the requirements.

Quality control should be applied to each stage of data processing to ensure that all data are credible and correctly processed.

12.2.2 Study monitoring

The authorized and qualified monitor will visit the clinical trial centers regularly according to the monitoring plan to verify the source data, the investigator's compliance with the protocol and regulations, and to assist the investigators.

12.2.3 Laboratory quality control

Each clinical trial center laboratory should establish unified standards for experimental test indicators, standard operating procedures and quality control procedures. Each experimental test item must adopt the national legal unit of measurement, and the test report items must be complete (including date, test item, test result and normal range), and relevant personnel should sign the report. Special inspection items must be specially assigned to be tested.

12.2.4 Quality control for other inspections

Each clinical trial center should establish unified evaluation criteria, standard operating procedures and quality control procedures for the evaluation of vital signs and damage. Each clinical trial center should evaluate the subject's condition according to the unified standard and standard operating procedures.

12.2.5 Qualification of study personnel

The investigators participating in the clinical trial must have the professional expertise, qualification and ability of clinical trials, and pass the qualification review. The personnel requirements shall be relatively fixed.

12.2.6 Study staff training before study initiation

The sponsor is responsible for the training of study personnel before the start of the trial to help the clinical study personnel get a full understanding and understanding of the overall situation of the trial, protocol, CRF, etc.

13. Ethical Issues and Informed Consent of Clinical Trial

13.1 Ethical Considerations

This clinical trial must be carried out in accordance with the *Declaration of Helsinki*, relevant medical device clinical trial regulations and laws in China. The study protocol must be approved by the Ethics Committee (EC) of the clinical trial institute before the study is initiated.

Before each subject is enrolled in the study, the study physician is responsible for explaining the contents of the trial to the subject in a verbal or written language understandable to the subject and carefully answering the subject's questions. Each subject must be given a written subject informed consent prior to enrollment. It is the responsibility of the study physician to obtain informed consent prior to each subject entering the study and to retain it in the study file.

This study is conducted based on the *Declaration of Helsinki*, *Good Manufacturing Practice* (GMP) for medical devices, *International Conference on Harmonisation Good Clinical Practice* (ICH-GCP), applicable laws and regulations in the People's Republic of China.

Based on ethical considerations, in accordance with ICH-GCP, relevant laws and regulations applicable within the territory of the People's Republic of China, the design and implementation of this study put the safety of subjects first on the requirements that the study medical device must be tested firstly when used under clinical conditions. Therefore, in this pre-clinical study, the biological safety of the materials used is tested firstly, and the purpose is to minimize the potential risks in the use of the materials. In order to fundamentally elucidate safety issues, various criteria for this study are also identified.

13.2 Approval of Study Protocol

Before the clinical trial, the investigators should submit the study protocol, informed consent form and other relevant documents to the medical ethics committee of the hospital where the study site is responsible for. The clinical trial can only be initiated after obtaining the approval of the Ethics Committee. Any amendment to the study protocol must be approved by the Ethics Committee before implementation. Serious adverse events during the clinical trial should be reported to the Ethics Committee in written form in a timely manner.

13.3 Informed Consent Process and Informed Consent Form Text

Before each subject is enrolled in this study, the investigators are responsible for introducing the contents and description of the informed consent form to him/her or his/her guardian completely and comprehensively in written form.

The informed consent form should be written in a language understandable to the subject or his/her guardian. The informed consent form shall contain no content that may cause the subject to give up his/her legal rights and interests, and that exempt the clinical trial institution, the investigators, the sponsor or his/her agent from taking the responsibilities.

Each subject must be given a written subject informed consent prior to enrollment. It is the responsibility of the investigators to obtain informed consent before each subject enters the study and to retain it in the study file.

For an incapacitated subject, if the Ethics Committee agrees in principle and the investigators believe that the subject's participation in the clinical trial is in his/her own interests, he/she can also enter the clinical trial, but his/her guardian should sign and date it before the trial.

When the subject or his/her guardian is unable to read, a witness shall be present during the process of

informed consent. After the informed consent form is explained in detail, the witness reads the informed consent form, which shall be consistent with the oral informed consent. After the subject or his/her guardian gives oral consent, the witness signs and dates the informed consent form, and the signature of the witness shall be on the same day as that of the investigator.

See the Informed Consent Form for details.

13.4 Personal Data and Data Protection

- (1) All data obtained in clinical trials are subject to data protection. The investigators should not disclose the subject's name and other personal data (excluding date of birth/age and gender).
- (2) The CRFs and other documents transmitted to the sponsor will not contain names, but only the study code of the subject.
- (3) Similarly, the data used for statistical evaluation can only be performed under the study code of the subject. Only the investigator can identify the subject's name and other personal information through the study code.
- (4) During the study, if the subject name needs to be identified for medical reasons, all relevant personnel are obligated to keep it confidential.

14. Provisions for Reporting Adverse Events and Device Defects

14.1 Adverse Event

14.1.1 Definition of adverse events

Adverse event (AE): refers to any adverse medical event occurring in the clinical trial process, no matter whether it is related to the investigational medical device or not.

14.1.2 Adverse event grading

- (1) Mild: Symptoms inquired.
- (2) Medium: Symptoms that are actively described but can be tolerated.
- (3) Severe: Intolerable symptoms with objective manifestations.

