8.1.3 Selection of test method and reasons

This clinical trial is a "prospective, multi-center, stratified-block randomization, incomplete blinding, parallel

positive control, non-inferiority test".

- (1) Prospective: A research method that tracks from the present to the future. Prospective studies can clarify the causal relationship; uniform diagnostic, detection, and evaluation criteria can be available for the obtained data, the data processing therefore is controllable.
- (2) Multi-center: 5 clinical trial institutions were selected to conduct this clinical trial. The application of multi-center trial can allow to obtain more cases than those of single-center trial in the same time, the clinical trial time therefore can be shortened; since the multi-center trial is completed by different regions, different trial centers and many clinical researchers, the conclusion therefore is often widely representative.
- (3) Stratified block randomization: This trial adopts the stratified block randomization method (with the study site as the stratification factor) and the randomization envelope to randomize the subjects who are screened successfully. The randomized-grouping time is when the subjects sign the ICF, which also meets the inclusion and exclusion criteria in the protocol at the same time. Randomized grouping ensures that, except for treatment factors, other non-treatment factors that may have confounding effect are kept consistent in each group as far as possible, so as to ensure the balance of baseline of each group; randomized-grouping allows each subject to have equal opportunity to be assigned to the test group or control group.
- (4) Incomplete blinding: Since the investigational medical device and the control medical device are different in appearance, while the subjects are under anesthesia during the operation, the grouping arrangement can not be known. Therefore, the method of incomplete blinding is used, that is, the investigators knows the grouping result, while the subject does not know the grouping result. The blinding method can minimize the bias caused by "placebo effect" and investigator bias; for the less precise observation indicators, it can significantly reduce the bias; and make the evaluation of adverse reactions by investigators and subjects more objective.

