8.1.16 Safety evaluation method

(1) Incidence of anastomotic stoma dehiscence

Justification for selection: When stapler is used for intestinal anastomosis, it is necessary to select appropriate reload. Dehiscence of the anastomotic stoma may increase the risk to the subject. Therefore, the "incidence of anastomotic stoma dehiscence" is selected as one of the safety indicators of the product under evaluation. At the same time, with reference to the *Guidelines for Technical Review of Endoscopic Stapler Registration* issued by NMPA (original CFDA) on March 13, 2017, the "incidence of anastomotic stoma dehiscence" is selected as a safety evaluation indicator for such products.

Evaluation time: During the surgery.

Evaluation method: Anastomotic stoma dehiscence due to "staple popping" during surgery is recorded.

Formula: Incidence rate of anastomotic stoma dehiscence = number of eligible subjects in each group/total number of subjects in the group \times 100%

(2) Incidence of anastomotic stoma bleeding

Justification for Selection: Anastomotic stoma bleeding is a common complication in gastrointestinal anastomosis procedures, which will increase the risk to subjects. Therefore, "the incidence of anastomotic stoma bleeding" is selected as one of the indicators to evaluate the product safety. Meanwhile, with reference to the *Guidelines for Technical Review of Endoscopic Stapler Registration* issued by NMPA (original CFDA) on March 13, 2017, the "incidence rate of anastomotic stoma bleeding" is selected as a safety evaluation indicator for such products.

Evaluation time: from the end of surgery to the end of follow-up.

Evaluation method: Alimentary tract bleeding occurs after operation, and is confirmed as the anastomotic stoma source by observing digestive cavity decompression tube and intraperitoneal drainage tube, endoscope and angiography. If the source is not identified, it is then called gastrointestinal bleeding.

Formula: Incidence rate of anastomotic stoma bleeding = number of eligible subjects in each group/total number of subjects in the group \times 100%

(3) Incidence of anastomotic leakage

Justification for selection: Anastomotic leakage is a common complication of gastrointestinal anastomosis, which will increase the risk to subjects. Therefore, the "incidence of anastomotic leakage" is selected as one of the safety indicators for product evaluation. At the same time, with reference to the *Guidelines for*

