Technical Review of Endoscopic Stapler Registration issued by China Food and Drug Administration on March 13, 2017, the "incidence of anastomotic leakage" is selected as a safety evaluation indicator for such products.

Evaluation time: From the end of surgery to the end of follow-up.

Evaluation method: Patients with at least one of the following items are considered as anastomotic leakage: A. imaging examination, such as gastrointestinal radiography, confirms anastomotic leakage; B. fecal substances appearing in the abdominal drainage tube or incision, in which other sources of intestinal tract can be excluded; C. reoperation exploration confirms anastomotic leakage; D. abdominopelvic abscess beside the anastomosis. Anastomotic leakage is divided into 3 grades according to the severity: Grade A: no special treatment is required; Grade B: active treatment is required, but no reoperation is required; Grade C: reoperation is required.

Formula: Incidence of anastomotic leakage = eligible subjects in each group/total number of subjects in this group \times 100%

Precautions: Necessary records should be kept for the treatment of anastomotic leakage.

(4) Incidence of anastomotic stricture

Justification for Selection: Anastomotic stricture is a common complication of gastrointestinal anastomosis, which will increase risks to subjects. Therefore, "the incidence of anastomotic stricture" is selected as one of the indicators to evaluate the product safety.

Evaluation time: From the end of surgery to the end of follow-up.

Evaluation method: The clinician judges whether the subject has an anastomotic stricture based on the symptoms, signs, endoscopy, angiography, etc.

Formula: Incidence rate of anastomotic stricture = eligible subjects in each group/total number of subjects in the group \times 100%

(5) Incidence of anastomotic stricture infection

Justification for Selection: Anastomotic stricture infection is a common complication of gastrointestinal anastomosis, which will increase risks to subjects. Therefore, "the incidence of anastomotic stricture infection" is selected as one of the indicators to evaluate the product safety.

Evaluation time: from the end of surgery to the end of follow-up.

Evaluation method: The clinician judges whether the subject has a staple line infection based on the symptoms, signs, endoscopy, angiography, etc.

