Formula: Incidence rate of anastomotic stricture infection = eligible subjects in each group/total number of subjects in the group \times 100%

(6) Incidence of SAE (serious adverse event)

Evaluation time: During the whole clinical trial process.

Evaluation method: Serious adverse event refers to an event occurs in the process of clinical trials, which results in death or serious deterioration of health, including fatal disease or injury, permanent damage to the body structure or function, requiring hospitalization or prolonging the hospitalization, requiring medical or surgical intervention to avoid the permanent damage to the body structure or function; results in fetal distress, fetal death or congenital abnormality, congenital defect, etc.

Formula: SAE incidence = number of subjects with SAE in this group/number of all subjects in this group \times 100%.

Precautions: The adverse events related to the anastomotic stoma during clinical trial shall be considered as serious adverse events. Since "anastomotic stoma repair" may be associated with "anastomotic stoma dehiscence", the "anastomotic stoma repair "is not repeatedly considered a serious adverse event.

(7) Incidence of AE (adverse event)

Evaluation time: During the whole clinical trial process.

Formula: Incidence of adverse events = number of subjects with adverse events in this group/number of all subjects in this group \times 100%.

Definition: An adverse event is any untoward medical occurrence in a clinical investigation, whether or not related to the device. It is necessary to analyze the postoperative vital signs and laboratory tests (blood routine, biochemical indicators, etc.).

(8) Incidence of device defects

Measurement time: During the whole process of clinical trial.

Calculation formula: Incidence of device defect = number of device defects/total number of devices × 100%.

Precautions: A test device defect that occurs during the course of a clinical trial. "Staple pop" due to human factors (e.g., incorrect reload selection) is not a defect of the device.

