14.1.5 Handing protocol of adverse events that may occur in this clinical trial

- (1) Anastomotic bleeding: It is related to the factors of anastomotic leakage. The bleeding is generally the technical factor. The prevention is mainly to avoid the tension at the anastomotic stoma and the fat drop left at the cutting site.
- (2) Anastomotic leakage: The incidence of anastomotic leakage is reported to be 4% to 15% in the literature. It may be caused by the stapler, or related to the patient's condition or the doctor's operation;
- (3) Anastomotic stricture: It is one of the most common complications, mostly occurring after 1 month after surgery.
- (4) Major incisional bleeding: Drop in hemoglobin $\geq 20g/l$ resulting in ≥ 1 transfusion.
- (5) Minor incision bleeding: Bleeding that does not meet the criteria for "severe bleeding".
- (6) Incision site infection: Infection at the incision site due to improper nursing, resulting in prolonged incision healing time, prolonged suture removal time, or unplanned antibiotic therapy.
- (7) Delayed healing of incision: The incision in contact with suture has delayed healing time.
- (8) Anemia and hypoproteinemia: Symptoms caused by tumor deterioration in patients with gastric cancer;
- (9) Tumor recurrence or metastasis: Symptoms caused by further tumor deterioration in patients with gastric cancer;

(10) Gastrointestinal discomfort symptoms: Common symptoms of gastrointestinal diseases, such as nausea, belching, constipation, diarrhea, acid reflux, abdominal pain, etc.

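### The only general adverse event severity scale grades reported symptoms, so intraoperative dehiscence and symptomless laboratory or sign-only events have no valid grade

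*Combined protocol and SAP*

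**What the plan says.** Section 14.1.2 defines three grades: "Mild: Symptoms inquired"; "Medium: Symptoms that are actively described but can be tolerated"; and "Severe: Intolerable symptoms with objective manifestations". No other severity scale in the protocol covers adverse events in general.

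Section 14.1.1 counts any adverse medical event as an adverse event, and 14.1.3 asks for a severity for all adverse and serious adverse events.

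Section 8.1.16(1) assesses dehiscence at one time only: "Evaluation time: During the surgery". Section 8.1.3(4) says of that period that "while the subjects are under anesthesia during the operation, the grouping arrangement can not be known".

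Under the adverse event indicator, 8.1.16(7) adds: "It is necessary to analyze the postoperative vital signs and laboratory tests (blood routine, biochemical indicators, etc".

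Leakage alone has a severity grade based on consequence, in 8.1.16(3): "Grade A: no special treatment is required; Grade B: active treatment is required, but no reoperation is required; Grade C: reoperation is required".

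Section 14.1.5(4) defines Major incisional bleeding by a haemoglobin drop and transfusion. Item (5) then reads "Minor incision bleeding: Bleeding that does not meet the criteria for" severe bleeding, a term that 14.1.5 does not define.

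**The concern.** A severity field should separate trivial from grave events in the same way whatever the event type. This one works only for complaints that a conscious subject can voice. Several events that matter in a stapler trial are found by looking or measuring, so they fall outside the definitions while the field must still be filled.

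The severity column would then mix grades that follow the definitions with improvised ones. A reader comparing the two devices by grade could be misled, because the grade does not track what an event led to.

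**Working it through.** The plan states no figure on this point and gives no expected rate for dehiscence or laboratory events, so the check sets the passages side by side.

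**1. Which events need a grade.** All of them, by 14.1.1 with 14.1.3. Section 8.2.9 adds that required case report form fields may not be left blank.

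**2. What each grade needs.** Mild needs a symptom found on questioning. Medium needs a symptom the subject volunteers and can bear. Severe needs a symptom the subject cannot bear and, in addition, an objective finding. That finding is an extra condition, not a second route into the grade.

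**3. The grades applied to events in the plan.**
- *Dehiscence.* It is recorded intraoperatively, under anaesthesia. Nothing can be asked, volunteered or tolerated, so no grade applies. Dehiscence has no scale of its own and is one of the five anastomotic safety indicators in the protocol abstract.
- *Symptomless laboratory event*, such as a low haemoglobin or albumin. No grade applies. However extreme the value, it cannot be Severe without an intolerable symptom. Anaemia and hypoproteinaemia are foreseen events in 14.1.5(8).
- *Other sign-only event.* The result is the same.
- *Leak seen only on imaging.* It has a grade A, B or C under 8.1.16(3), but no rule turns that letter into Mild, Medium or Severe.
- *The same tolerable symptom in two subjects.* It is Mild if the investigator asks first and Medium if the subject speaks first. By 8.1.3(4) and 8.2.4 the investigator knows the arm, so a difference in how actively subjects are questioned can shift grades between arms with no clinical difference.

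**4. Whether seriousness fills the gap.** It does not. Section 8.1.16(6) makes every adverse event related to the anastomosis serious. Seriousness therefore cannot separate an anastomotic bleed, stricture or infection that needed nothing from one that needed reoperation. Outside leakage, 14.1.2 is the only severity measure for these events.

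**5. Where the grade is used.** The incidence formulas in 8.1.16(6) and (7) count subjects with an event, whatever its grade. Section 9.7.1 asks for frequencies and percentages for enumeration data across all safety data, plus an adverse event listing. Severity enters there and nowhere else in the documents.

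**The case against.** The strongest reply is that little depends on this field. No analysis by grade is specified, and what the grade misses is largely recorded elsewhere: treatment given for each event (14.1.3), hospitalisation or intervention through the serious adverse event definition (14.2.1), reoperation for a leak as Grade C, and dehiscence through its own incidence and the repair stitch count. This stands, and it limits the size of the point. It does not make the field valid, and none of these records is mapped to a grade.

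One can also say that the protocol uses the word symptom loosely. Section 14.1.5 applies it to anaemia and hypoproteinaemia. Even so, a laboratory value cannot be elicited by questioning, described by the subject or found intolerable.

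Three stronger readings are tempting, and the documents do not support them:
- *Leaks found only on imaging have no severity grade.* Section 8.1.16(3) grades every leak by what it required. Nor would applying the 4% to 15% leak incidence in 14.1.5(2) to the arm size measure misgrading. It would only count expected leaks.
- *A transfused bleed with tolerable symptoms is both Major and Minor.* This needs severe bleeding in 14.1.5(5) to mean the Severe grade of 14.1.2. Item (5) directly follows the definition of Major bleeding and evidently refers to it. The fault is one of terminology.
- *The trial would miss an excess of transfusions or reoperations.* The treatment records named above would still hold them. Only a comparison by grade could fail to show it.

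**Conclusion.** The point holds in limited form. The scale in 14.1.2 gives no valid grade to intraoperative dehiscence, symptomless laboratory events or other sign-only events. It separates Mild from Medium by who spoke first, with an unblinded investigator asking. The leak grades are sound but unconnected to it.

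The damage is confined to the adverse event listing and the descriptive safety summary. The primary endpoint, the safety incidences, the hypothesis tests, the sample size and the pass criterion are untouched. How many entries would be affected cannot be estimated from the documents.

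The conclusion assumes that 14.1.2 is applied as written and that the separate statistical analysis plan announced in 9.1 does not redefine severity. It is still worth correcting, because the trial compares device safety for registration and the remedy uses data already collected.

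**What to change.** Replace 14.1.2 with one consequence-based scale for all adverse events, matched one to one to leak grades A, B and C:
- Grade 1: the event needed no special treatment.
- Grade 2: it needed active treatment but no reoperation. This includes an event corrected within the index operation and any non-operative procedure.
- Grade 3: it needed reoperation.

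State that the scale applies to intraoperative and laboratory events. Keep life-threatening or fatal outcome under the serious adverse event definition in 14.2.1, and read the grade beside that field. Assign the grade from the treatment already recorded under 14.1.3. This classifies events and does not change how any event is managed.

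Reconcile the term severe bleeding in 14.1.5(5) with Major incisional bleeding in 14.1.5(4).

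The cost is revised protocol and case report form wording for one field, the ethics committee approval that 16.2 requires for such a revision, and brief site retraining. No new data are needed.
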